12 STATISTICAL AND ANALYTICAL PLANS

This section presents a summary of the planned final analyses for efficacy, safety, and clinical pharmacology. Efficacy and safety statistical analysis details will be provided in the statistical analysis plan (SAP) for this study, and clinical pharmacologic analysis details will be provided in the clinical pharmacology analysis plan (CPAP), both of which will be finalized before last subject last visit for the treatment period (Part A).

The primary endpoint analysis will occur after all subjects in Cohort 1 have completed the SFUV, and all related data have been locked.

An additional analysis for Part A will occur after all subjects in Cohort 2 have completed the SFUV and the related data have been locked.

The final analysis for the study will occur after all subjects have completed their last required visit of the study (Part A or Part B, as applicable) and the database has been locked.

12.1 Sample Size and Power

The sample size was not calculated based on power assumptions, because this is an estimation study. The primary endpoint is percent change from baseline in UPCR at Week 13. Assuming an SD of 0.672 (in log scale), ²⁵ a sample size of 10 subjects will provide a precision of 0.294 (in log scale) for the estimation of the Geometric Mean Percent Change (GMPC) from baseline in UPCR. The precision of the estimate corresponds to the half width of its 80% CI, in log scale. Table 12-1 displays the expected size of the 80% CIs for the GMPC at various values of the observed GMPC.

Table 12-1 Two-sided 80% Confidence Interval for GMPC from Baseline in UPCR

Number of		Observed GMPC (corresponding percent reduction from baseline)			
Subjects Completing	Assumption for SD in Log Scale	0.5 (-50%)	0.6 (-40%)	0.7 (-30%)	0.8 (-20%)
10	0.672	0.37, 0.67 (-63%, -33%)	0.45, 0.81 (-55%, -19%)	0.52, 0.94 (-48%, -6%)	0.60, 1.07 (-40%, 7%)

12.2 Analysis Sets

The following analysis sets are defined: All Subjects Set, Full Analysis Set (FAS), Safety Set, and Follow-up Set.

The **All Subjects Set** will include all subjects who were enrolled in the study. This analysis set will be used for all individual subject data listings and disposition summary tables, unless otherwise specified.

The **FAS** will include all subjects who received at least 1 dose of study drug in the Treatment Period and at least 1 post-baseline efficacy assessment. The FAS will be used for all efficacy analyses in the Treatment Period, unless otherwise specified.

The **Follow-up Set** will include all subjects who entered the Off-treatment Follow-up Period (Part B) and have at least 1 efficacy assessment in that period. The Follow-up Set will be used for all efficacy analyses in the Follow-up Period, unless otherwise specified.

The **Safety Set** will include all subjects who received at least 1 dose of study drug. The Safety Set will be to summarize subject demographics and baseline characteristics, and used for all safety analyses, unless otherwise specified.

12.3 Statistical Analysis

This section presents a summary of the planned statistical analyses of efficacy, safety and PK endpoints of the study. Statistical analysis details will be provided in the SAP.

12.3.1 General Considerations

Continuous variables will be summarized using the following descriptive summary statistics: the number of subjects (n), mean, SD, median, minimum value (min), and maximum value (max). The precision of the measurement for each continuous variable will be specified in the SAP. Unless otherwise specified, minimum and maximum values will be reported with the same precision as the units of the raw data. The mean, median, and SD will be reported to 1 additional decimal place. Any values that require a transformation to standard units (metric or International System [SI]) will be converted with the appropriate precision.

Categorical variables will be summarized using counts and percentages. Percentages will be presented to 1 decimal place.

Baseline value, unless specified otherwise, will be defined as the most recent non-missing measurement (scheduled or unscheduled) collected before the first dose of study drug in the Treatment Period (i.e., the Day 1 Visit). For ECGs, baseline will be defined as the most recent pretreatment measurement (or the average of triplicate measurements, if the most recent pretreatment measurement is obtained in triplicate) before the first dose of study drug in the Treatment Period (i.e., the Day 1 visit). For UPCR (and UACR) data baseline value will be the average of UPCR (UACR) values from the 3 urine samples collected during screening for the purpose of assessing eligibility.

Change (absolute change) from baseline will be calculated as Post-baseline value – Baseline value.

Treatment-emergent (TE) Period will include the time from the first dose of study drug in the Treatment Period to either (1) the SFUV, (2) ETT Visit if it replaces the SFUV, or (3) the date of the last dose + 28 days for subjects who do not have a SFUV. The TE Period will be used for safety analyses unless specified otherwise.

The analysis visit windows for protocol-defined visits will be described in the SAP.

The rules for handling missing data due to treatment or study discontinuation will be described in the SAP.

Data will be analyzed separately for the Treatment Period (Part A) and the Off-treatment Follow-up Period (Part B), unless specified otherwise.

12.3.2 Background Characteristics

12.3.2.1 Subject Disposition

The number and percentage of subjects in each disposition category in the Treatment Period (e.g., included in the All Subjects Set, included in the Safety Set, completed Treatment Period, completed SFUV, and discontinued treatment or study with a breakdown of the reasons for discontinuation) will be summarized.

The number and percentage of subjects in each disposition category in the Off-treatment Follow-up Period (e.g., included in the Follow-up Set, completed Follow-up Period, and discontinued study/Follow-up Period with a breakdown of the reasons for discontinuation) will be summarized.

12.3.2.2 Demographics and Baseline Characteristics

Demographics, background (e.g. medical history), and baseline characteristics will be summarized using descriptive summary statistics.

The following demographics and baseline characteristics will be summarized based on the Safety Set and will include (but not limited to): sex, race, age, weight, height, BMI, UPCR, UACR, and eGFR.

12.3.2.3 Prior and Concomitant Medications

Medications used will be coded using the World Health Organization-Drug Dictionary (WHO-DD) and categorized as the following:

Prior medication: any medication that started before the date of the first dose of study drug, regardless of when the medication ended

Concomitant medication: medication continued or newly received on or after the date of the first dose of study drug through the end of the TE Period

A given medication may be classified as prior, concomitant, or both prior and concomitant.

If a medication start date is on or after the first dose date of study drug, then the medication will be categorized as concomitant medication regardless of whether the medication end date is missing or not. If a medication end date is before the first dose date of study drug, then the medication will be categorized as prior medication regardless of whether the medication start date is missing or not. Note that medication that started before the first dose of study drug and continued after the first dose will be categorized as prior medication and separately as concomitant medication.

If a medication has a missing or partially missing start/end date or time and if it cannot be determined whether it was taken before the first dose of study drug, or concomitantly, it will be considered in both categories of prior and concomitant medication.

Prior medications and concomitant medications will be summarized descriptively using frequency tables by Preferred Name based on the Safety Set.

Details for imputing missing or partial start and/or stop dates of medication will be in the SAP.

12.3.2.4 Study Drug Exposure and Compliance

Exposure to study drug will be summarized for the Safety Set in terms of duration of treatment a subject received (in days), defined as: last dose date – first dose date + 1 day, regardless of study drug interruption.

Study drug compliance based on study drug exposure, will be summarized for the Safety Set, and will be calculated as: $100 \times [1 - (\text{total number of days of any study drug interruption})/(\text{duration of study drug exposure in days})].$

12.3.2.5 Important Protocol Deviations

An important protocol deviation (IPD) is a deviation that may significantly affect the completeness, accuracy, or reliability of the study data or that may significantly affect a subject's rights, safety, or well-being. The rules for identifying an IPD will be described in the SAP.

IPDs will be provided in an individual subject data listing.

12.3.3 Efficacy Analysis

Analyses will be done separately for Cohort 1 and Cohort 2.

12.3.3.1 Analysis of Primary Variables

The primary efficacy endpoint is percent change from baseline in UPCR at Week 13. The Week 13 UPCR value will be calculated as the average of the available UPCR measurements (maximum 3) taken during Week 13. The baseline value will be the average of the 3 UPCR values from the urine samples collected during screening.

The percent change from baseline in UPCR at Week 13 will be analyzed by first log-transforming the UPCR data before analyses to reduce skewness, and calculating the change from baseline in log-transformed values. The GMPC from baseline in UPCR will be estimated along with the corresponding 2-sided 80% CI. The GMPC from baseline and associated confidence limits will be calculated by back-transforming the estimated simple mean of change from baseline in log-transformed data.

Sensitivity analyses for handling missing data due to treatment or study discontinuation will be described in the SAP.

12.3.3.2 Analysis of Other Variables

In all exploratory analyses of UPCR and UACR related data, the Week 9 and Week 13 UPCR/UACR value will be calculated as the average of the available UPCR/UACR measurements (maximum 3) taken during Week 9 or Week 13, and the baseline value will be the average of the 3 UPCR/UACR values from the urine samples collected for this purpose during screening.

The percent change from baseline in UPCR over time during the Treatment period is an exploratory efficacy endpoint. Similar to the primary endpoint analysis, UPCR data will be log-transformed and change from baseline at each planned visit, up to Week 13, will be analyzed using the log-transformed UPCR values. The GMPC from baseline and associated 2-sided 80% CI at each planned visit will be calculated by back-transforming the corresponding estimated simple mean and CI from the log-transformed data.

Other exploratory efficacy endpoints include percent change from baseline in urinary albumin-to-creatinine ratio (UACR) at Week 13, and percent change from baseline in UACR over time during the Treatment period. Analysis of these 2 endpoints will be similar to that performed for the corresponding UPCR endpoints.

Off-treatment Follow-up Period (Part B): The exploratory endpoint of percent change from baseline in UPCR at the end of the Off-treatment Follow-up Period will be analyzed similarly to the primary efficacy endpoint.

Additional details of these analyses will be provided in the SAP.

12.3.4 Safety Analysis

All safety analyses will be based on data from the TE Period for all subjects in the Safety Set.

The overall safety profile of study drug will be assessed in terms of the following safety and tolerability endpoints:

- Incidence of treatment-emergent adverse events (TEAEs)
- Clinical laboratory values (hematology, serum chemistry, coagulation studies, and urinalysis)
- Standard 12-lead ECG outcomes
- Vital signs

Only a descriptive analysis of safety will be performed.

All safety data will be presented in individual subject data listings.

12.3.4.1 Adverse Events

For analysis purposes, AEs will be classified as pretreatment AEs or TEAEs, defined as follows:

Pretreatment AE: any AE that started before the first dose date of study drug

TEAE: any AE that worsened (either in severity or seriousness) or that was newly developed on or after the first dose date of study drug through the end of the TE Period

For AEs with completely missing or partially missing start dates, if there is no clear evidence that the AEs started before or after study treatment, the AEs will be classified as TEAEs.

AE summary tables will be presented for TEAEs only and will include the following:

- All TEAEs
- TEAEs by strongest relationship
- TEAEs by maximum severity
- TEAEs leading to treatment discontinuation
- Serious TEAEs
- TEAEs leading to death

Summaries will be presented by MedDRA System Organ Class (SOC) and Preferred Term (PT) using frequency counts and percentages (i.e., number and percentage of subjects with an event).

When summarizing the number and percentage of subjects with an event, subjects with multiple occurrences of the same AE or a continuing AE will be counted once. Only the maximum severity level will be presented in the severity summaries, and the strongest relationship level will be presented in the relationship summaries.

In addition, a listing of individual subject level AE data for TEAEs leading to treatment discontinuation, serious adverse events (SAEs), and deaths will be provided separately. All AEs, including pretreatment AEs, will be in individual subject data listings.

12.3.4.2 Clinical Laboratory Assessments

For treatment-emergent laboratory measurements, the observed values and change from baseline values of the continuous hematology, chemistry, and coagulation results will be summarized in SI units by visit.

The number and percentage of subjects with at least 1 laboratory event outside threshold criteria for the event during the TE Period will be summarized, including a shift of the event from baseline to post-baseline. The threshold criteria will be in the SAP.

Results of urinalysis and the urine/serum pregnancy test will be in individual subject data listings only.

In addition, a listing of individual subject hematology, chemistry, and coagulation values outside the normal reference ranges will be provided. This listing will include data from both scheduled and unscheduled visits.

12.3.4.3 Electrocardiogram

For treatment-emergent ECG measurements, a summary of observed values and change from baseline values will be provided by visit and time point, as applicable, for the following ECG measurements: RR (msec), heart rate (HR; beats per minute [bpm]), PR (msec), QRS duration (msec), QT (msec), and QT corrected for HR intervals (QTcF [msec]).

The number and percentage of subjects meeting a threshold analysis criterion during the TE Period will be summarized. The threshold analysis criteria will be provided in the SAP.

Clinically significant abnormal findings will be reported as AEs.

Additional ECG analyses may be described in the SAP.

12.3.4.4 Vital Signs

For treatment-emergent vital signs measurements, the observed values and change from baseline values will be summarized by visit: systolic and diastolic blood pressure (mm Hg), body temperature (°C), pulse rate (bpm), and respiratory rate (breaths per minute).

The number and percentage of subjects with at least 1 event outside the threshold criteria for a vital sign during the TE Period will be summarized. The threshold analysis criteria will be provided in the SAP.

Clinically significant abnormal findings in vital signs will be reported as AEs.

Additional vital signs analyses may be described in the SAP.

12.3.4.5 Physical Examination

PE findings will be presented in individual subject data listings only.

12.3.4.6 Other Safety Analysis

Change from baseline in weight will be summarized by visit.

12.3.5 Other Analyses

Analysis of the exploratory endpoints for SF-36 will be provided in the SAP.

12.3.6 Interim and Independent Data Monitoring Committee Analyses

Interim analyses may be done at the discretion of the sponsor to allow for regulatory interactions and clinical development planning. There is no independent Data Monitoring Committee for this study.

12.4 Clinical Pharmacology Analysis

The following systemic exposure parameters will be estimated using noncompartmental and population PK analysis: AUCτ during a dosing interval, C_{max} and C_{trough} will be estimated for all subjects who provide adequate number of PK samples:

- on Day 1 after single administration of the lower dose;
- at Week 2 after the first administration of the higher dose;
- at Week 5 after multiple administrations of the higher dose.

In addition, observed C_{trough} will be reported at Weeks 1, 3, 9, and 13. Based on availability of data after the last administration of the higher dose, half-life will be reported after multiple administrations of the higher dose.

12.4.1 Pharmacokinetic Analysis

Mean and/or median plasma concentrations versus time will be plotted on log and linear scales. The PK parameters (C_{max} , C_{trough} , AUC_{τ} , and other parameters as needed) of VX-147 estimated by noncompartmental analysis will be listed and summarized using summary statistics. Ongoing analyses of plasma concentrations of VX-147 may be conducted before database lock.

Details of the analyses will be in the CPAP.

12.4.2 Pharmacokinetic/Pharmacodynamic Analyses

A population PK analysis of plasma concentration versus time data of VX-147 will be performed using the nonlinear mixed-effects modeling approach. Population and individual PK parameters: clearance after oral administration (CL/F) and apparent volume of distribution at steady state (Vss/F) will be estimated and the influence of various covariates (such as age, gender, and body weight) on these parameters will be investigated in an exploratory way. If deemed necessary, data may be pooled with data from other studies with VX-147 in order to improve the parameter estimates from the model.

Plasma concentration – response relationship (PD markers and AEs, if any) will be explored. A more detailed description of the methodology to be followed will be in either the CPAP or the population PK/PD analysis plan. Listings of VX-147 plasma concentration data will be in the bioanalytical report. The population PK analysis will be in a stand-alone report.

13 PROCEDURAL, ETHICAL, REGULATORY, AND ADMINISTRATIVE CONSIDERATIONS

13.1 Adverse Event and Serious Adverse Event Documentation, Severity Grading, and Reporting

13.1.1 Adverse Events

13.1.1.1 Definition of an Adverse Event

An AE is defined as any untoward medical occurrence in a subject during the study; the event does not necessarily have a causal relationship with the treatment. This includes any newly occurring event or worsening of a pre-existing condition (e.g., increase in its severity or frequency) after the ICF is signed.

An AE is considered serious if it meets the definition in Section 13.1.2.1.

13.1.1.2 Clinically Significant Assessments

Study assessments including laboratory tests, ECGs, PEs, and vital signs will be assessed and those deemed to have clinically significant worsening from baseline will be documented as an AE. When possible, a clinical diagnosis for the study assessment will be provided, rather than the abnormal test result alone (e.g., urinary tract infection, anemia). In the absence of a diagnosis, the abnormal study assessment itself will be listed as the AE (e.g., bacteria in urine or decreased hemoglobin).

An abnormal study assessment is considered clinically significant if the subject has 1 or more of the following:

- Concomitant signs or symptoms related to the abnormal study assessment
- Further diagnostic testing or medical/surgical intervention
- A change in the dose of study drug or discontinuation from the study

Repeat testing to determine whether the result is abnormal, in the absence of any of the above criteria, does not necessarily meet clinically significant criteria. The determination of whether the study assessment results are clinically significant will be made by the investigator.

A laboratory value that is Grade 4 will not automatically be an SAE. A Grade 4 laboratory value will be an SAE if the subject's clinical status indicates a life-threatening AE.

13.1.1.3 Documentation of Adverse Events

All AEs will be collected from the time the ICF is signed until the following times:

- For subjects who do not enroll: until time of screen failure (e.g., screen failure, withdrawal of consent)
- For enrolled subjects who have a SFUV: through the SFUV
- For enrolled subjects who do not have a SFUV, the earliest of
 - o 28 days after the last dose of study drug, or
 - o the ETT Visit, if that visit is 3 weeks or later following the last dose of study drug (see Section 9.1.2.3)

All subjects will be queried, using nonleading questions, about the occurrence of AEs at each study visit. When possible, a constellation of signs and/or symptoms will be identified as 1 overall event or diagnosis. All AEs for enrolled subjects will be recorded in the CRF and source document. AEs for subjects who are screened but not subsequently enrolled will be recorded only in the subject's source documents. The following data will be documented for each AE:

- Description of the event
- Classification of "serious" or "nonserious"
- Date of first occurrence and date of resolution (if applicable)
- Severity
- Causal relationship to study drug(s)
- Action taken
- Outcome
- Concomitant medication or other treatment given

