9.1.2.3 Early Termination of Treatment or Early Discontinuation

If a subject prematurely discontinues study treatment, an Early Termination of Treatment (ETT) Visit should be scheduled as soon as possible after the subject decides to terminate study treatment. Subjects who prematurely discontinue treatment will also be required to complete the SFUV, approximately $28 (\pm 7)$ days after their last dose of study drug. The assessments performed at the SFUV are listed in Table 3-3.

If the ETT Visit occurs 3 weeks or later following the last dose of study drug, then the ETT Visit will replace the SFUV, and a separate SFUV will not be required.

After the ETT Visit, subjects will not complete further Part A Visits; these subjects will not continue to Part B.

If a subject withdraws consent for the study, no further assessments will be performed. Vertex may retain and continue to use any data and samples collected before such withdrawal of consent.

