13.1.1.3 Documentation of Adverse Events

All AEs will be collected from the time the ICF is signed until the following times:

- For subjects who do not enroll: until time of screen failure (e.g., screen failure, withdrawal of consent)
- For enrolled subjects who have a SFUV: through the SFUV

- For enrolled subjects who do not have a SFUV, the earliest of
 - o 28 days after the last dose of study drug, or
 - o the ETT Visit, if that visit is 3 weeks or later following the last dose of study drug (see Section 9.1.2.3)

As noted in Table 3-1, for subjects undergoing a 2-step screening process, AEs related to phlebotomy will be collected for up to 24 hours after the blood collection; AEs will not be collected during the time between a subject undergoing genotype screening and the start of the Screening Visit.

All subjects will be queried, using nonleading questions, about the occurrence of AEs at each study visit. When possible, a constellation of signs and/or symptoms will be identified as 1 overall event or diagnosis. All AEs for enrolled subjects will be recorded in the CRF and source document. AEs for subjects who are screened but not subsequently enrolled will be recorded only in the subject's source documents. The following data will be documented for each AE:

- Description of the event
- Classification of "serious" or "nonserious"
- Date of first occurrence and date of resolution (if applicable)
- Severity
- Causal relationship to study drug(s)
- Action taken
- Outcome
- Concomitant medication or other treatment given

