9 STATISTICAL ANALYSIS

9.1 General Considerations

The Schedule of Assessments is provided in Section 3 of the CSP. The precision standards for reporting variables are provided in an internal Biometrics document that specifies the programming rules including the precision for derived variables.

Continuous variables will be summarized using the following descriptive summary statistics: the number of subjects (n), mean, SD, median, minimum value (min), and maximum value (max).

Categorical variables will be summarized using counts and percentages.

Baseline value, unless specified otherwise, will be defined as the most recent non-missing measurement (scheduled or unscheduled) collected before the first dose of study drug in the Treatment Period. For ECGs, baseline will be defined as the most recent pretreatment measurement (or the average of triplicate measurements, if the most recent pretreatment measurement is obtained in triplicate) before the first dose of study drug in the Treatment Period. For systolic and diastolic blood pressure, baseline will be defined as the most recent pretreatment measurement (or the average of triplicate measurements, if the most recent pretreatment measurement is obtained in triplicate) before the first dose of study drug in the Treatment Period. For UPCR (and UACR) data baseline value will be the average of UPCR (UACR) values from the 3 urine samples collected during screening for the purpose of assessing eligibility.

Change (absolute change) from baseline will be calculated as Post-baseline value – Baseline value.

Treatment-emergent (TE) Period will include the time from the first dose of study drug in the Treatment Period to either (1) the Safety Follow-up Visit, (2) ETT Visit if it replaces the Safety Follow-up Visit, or (3) the date of the last dose + 28 days for subjects who do not have a Safety Follow-up Visit. The TE Period will be used for safety analyses unless specified otherwise.

Unscheduled visits: Data obtained from unscheduled visits will be included in the analysis as follows:

- In scheduled visit windows per specified visit windowing rules
- In the derivation of baseline
- In the derivation of maximum and minimum values during TE period, and maximum and minimum change from baseline values during TE period for safety analyses
- In individual subject data listings as appropriate

Visit Window: The analysis visit windows for the protocol-defined visits are provided in [Appendix A](#).

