 - ii. If there are multiple measurements with the same distance from the target day, the latest measurement will be used. If the latest measurement cannot be determined, then unscheduled visit will be selected.
 - iii. If there are multiple measurements from the central laboratory and local laboratory with the same distance from the target day, the measurement from the central laboratory will be used.

³For measurements collected on the date of first dose of study drug in Treatment Period, if it cannot be determined whether the measurement is before or after the first dose:

- a. Scheduled measurement will be treated as pre-dose observation;
- b. Unscheduled measurement will be treated as post-dose observation.

⁴For safety assessment, the Safety Follow-up analysis visit will be based on nominal Safety Follow-up visit. If a subject doesn't have a nominal Safety Follow-up visit but has an ETT visit occurs 3 weeks (21 days) or later following the last dose of study drug, then the ETT visit will be mapped into Safety Follow-up analysis visit.

⁵UPCR and UACR at Week 5, Week 9 and Week 13 will be calculated by averaging maximum 3 nonmissing UPCR and UACR values measured within a 7-day period within the visit window.

- a. If there is only 1 assessment within the visit window, use the single value
- b. If there are more than 1 assessment within the visit window:
 - i. find the earliest assessment within the visit window, and then find the number of assessments within 7 days after the earliest assessment;
 - ii. find the second assessment within the visit window, and then find the number of assessments within 7 days after the second assessment;
 - iii. find the third assessment within the visit window, and then find the number of assessments within 7 days after the third assessment, if applicable;
 - iv. Compare the number of assessments from step i to iii, use the assessments from the step that has the maximum number. If number of assessments are the same from multiple steps, then use the step with the first assessment closest to target study day.

Derived Variable:

1. Missing first dose date or last dose date
 - If the first dose date is missing, use Day 1 visit date to impute.

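### When the ETT Visit that replaces the SFUV falls more than 28 days after the last dose, AE collection ends at Day +28 but the treatment-emergent period runs on to that visit

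*Protocol*

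**What the plan says.** All references are to Protocol Version 6.0 and the SAP. Version 2.0 of the protocol carries the same collection rule.

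- **Collection of AEs (Protocol 13.1.1.3).** Subjects with a SFUV have AEs collected through that visit. The rule for the others begins "For enrolled subjects who do not have a SFUV, the earliest of" and lists two dates: "28 days after the last dose of study drug, or" and "the ETT Visit, if that visit is 3 weeks or later following the last dose of study drug (see Section 9.1.2.3").
- **When the ETT Visit stands in for the SFUV (Protocol 9.1.2.3).** "If the ETT Visit occurs 3 weeks or later following the last dose of study drug, then the ETT Visit will replace the SFUV". No latest day is set. The "Visit should be scheduled as soon as possible after the subject decides to terminate study treatment", so its timing hangs on the decision to stop and not on the last dose.
- **TE period.** Protocol 12.3.1 ends it at "2) ETT Visit if it replaces the SFUV", and SAP 9.1 at "2) ETT Visit if it replaces the Safety Follow-up Visit". The 28-day limit applies only to subjects without a SFUV.
- **Use of the visit (SAP Appendix A, note 4).** If there is no nominal SFUV and the ETT Visit is at least 21 days after the last dose, "then the ETT visit will be mapped into Safety Follow-up analysis visit".
- **Other AE rules.** Protocol 13.1.1.3 also has subjects asked about AEs at every study visit. Protocol 13.1.1.2 requires clinically significant worsening in laboratory tests, ECGs, examinations and vital signs to be documented as an AE. Protocol 13.1.2.2 runs all-cause SAE reporting through the SFUV and asks only for related SAEs after it.

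**The concern.** The period over which events are counted should not be longer than the period over which they are collected. Protocol 12.3.4.1 and SAP 9.4.1 count events to the end of the TE period. If collection has closed earlier, the remaining days look event-free because nobody was required to record events in them. Laboratory, vital-sign and ECG findings from the same visit still enter the safety summaries as Safety Follow-up data.

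Two further points follow. A SFUV on Day 29 to 35 lies within its window and has AEs collected through it, while an ETT Visit replacing it on the same day does not; no reason is given. And sites face instructions that pull apart: collection has ended, yet AEs must be asked about at the visit and clinically significant worsening must be documented. Different sites could record the same event differently.

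**Working it through.** The check is on date rules; the plan gives no figure of its own to reproduce.

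**Inputs.** Let *d* be the day of the ETT Visit counted from the last dose.

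1. Replacement of the SFUV: *d* ≥ 21, no upper limit (Protocol 9.1.2.3).
2. End of AE collection when the SFUV is replaced: min(28, *d*) (Protocol 13.1.1.3).
3. End of the TE period in that case: *d* (Protocol 12.3.1, SAP 9.1).
4. SFUV window: 28 ± 7, that is Day 21 to Day 35.

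**Formula.** TE time without required AE collection = *d* − min(28, *d*) = max(0, *d* − 28).

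| ETT day *d* | AE collection ends | TE period ends | Gap (days) |
|---|---|---|---|
| 21 | 21 | 21 | 0 |
| 24 | 24 | 24 | 0 |
| 28 | 28 | 28 | 0 |
| 29 | 28 | 29 | 1 |
| 35 | 28 | 35 | 7 |
| 42 | 28 | 42 | 14 |
| 56 | 28 | 56 | 28 |

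An ETT Visit before Day 21 does not replace the SFUV. Both periods then end at the SFUV or, if it is missed, both at Day 28. The gap is 0 either way.

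The days above 28 are illustrations, because the documents set no maximum. At *d* = 42 the gap is 14/42 = 33% of the off-drug TE time.

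**Can *d* exceed 28?** Yes, by two routes.

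- Protocol 9.8 allows dosing to be interrupted for safety and states no maximum length. If a subject is interrupted for more than 4 weeks and then stops for good, even a prompt ETT Visit falls after Day 28.
- Visit spacing does not rule it out. The Week 5 Visit may be as early as Day 36 − 2 = 34 and the Week 9 Visit as late as Day 64 + 2 = 66, and 66 − 34 = 32 days.

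**After the fix.** Collection ends at *d* whenever the ETT Visit replaces the SFUV, so the gap is *d* − *d* = 0 for every *d* ≥ 21.

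**The case against.** The case against giving this weight is substantial, and most of it stands.

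- A reader might infer that every replacing ETT Visit, or every early stopper, leaves uncollected time. The table shows otherwise: up to Day 28 the two rules agree.
- A reader might infer that AEs are plainly not collected at the late ETT Visit. The documents do not support that. The query at every visit, the rule on clinically significant worsening, and the AE row of Table 3-2, which runs continuously through the SFUV, all point towards recording them. The text contradicts itself; it does not clearly exclude these events.
- A reader might infer that AE rates would be diluted. SAP 9.4.1 plans only numbers and percentages of subjects, with no exposure-adjusted rate, so the extra days enter no denominator. A table changes only if an event after Day 28 goes unrecorded and is the subject's sole occurrence of that term, or the one that sets the maximum severity or strongest relationship.
- A reader might infer that SAEs are lost after Day 28. Section 13.1.2.2 contains no 28-day stop. Without a SFUV its all-cause end point is undefined, which is a gap in the text and not a cut-off.
- The ETT Visit is meant to be prompt, so a visit after Day 28 should be uncommon.

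None of this removes the conflict. Where *d* exceeds 28, Section 13.1.1.3 and the TE definition give different end dates in the current protocol and SAP, and nothing says which governs.

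**Conclusion.** The inconsistency is real, narrow and of small expected effect. It arises only when the ETT Visit replaces the SFUV and falls more than 28 days after the last dose, and its length is max(0, *d* − 28) days. The number of such subjects is not given and is assumed to be small. With up to 10 subjects planned in Cohort 1 and about 10 in Cohort 2, one such subject is about 1/20 = 5% of the safety population. The documents do not support a claim that early stoppers in general have unobserved TE time, or that their events would necessarily be missed. They do support a correction, because the collection rule, the TE definition, the visit-query rule and the SAE end point do not fit together for these subjects.

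**What to change.** In Protocol 13.1.1.3, replace the rule for subjects without a SFUV with two entries:

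- enrolled subjects whose ETT Visit replaces the SFUV: collect AEs through the ETT Visit;
- enrolled subjects with neither visit: collect AEs until 28 days after the last dose.

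Use the same end points for all-cause SAE reporting in 13.1.2.2. AE collection then ends where the TE period ends, and the TE definition in Protocol 12.3.1 and SAP 9.1 can stay as it is.

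Capping the TE period at Day 28 would also close the gap, but it is the poorer choice: an ETT Visit after Day 28, which the SAP maps to Safety Follow-up, would then lie outside the TE period.

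The cost is protocol wording. No visit is added, since the ETT Visit takes place anyway and AEs are already asked about there.
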